### 9.2.1 Study time period

The study time period will be based on availability of information from the National Registries; this will start from 01 January 2007 in Sweden, 01 January 2010 in Norway, and 01 January 1997 (01 April 2004 for secondary outcome) in Denmark in order to allow for 24 months average look back period for live births:

- pregnancy duration (9-months on average for live births),
- maternal and paternal preconceptional exposure (3-months),
- minimum look back period for confounders (12-months).

The study time period ends on 31 December 2018 for Denmark and 31 December 2019 for Sweden and Norway. The rationale for this choice is to include all data available from relevant

 In Denmark, for the period 1997-1 April 2004, stillborns born between 22nd and 28th weeks of gestation are not included in the Medical Birth Register but in the National Patient Register. However, since in the National Patient Register the linkage with the father is not available, the study period for the secondary outcome in Denmark is limited to 2004-2017 (or last available date).

linked registers, to capture a sufficient number of outcomes and exposures and linked family units, and to include the most up-to-date data available.

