#### 9.3.2.1 Neurodevelopmental disorders, including ASD

The **index date** will be defined as the birth date of the offspring from which offspring will be observed for occurrence of the outcome of interest.

The **exit date/end of follow-up** will be defined as the end of the study period (31 December 2018 for Denmark and 31 December 2019 for Sweden and Norway), death, emigration (where available), reaching the age of 12 years for Denmark and Sweden and the age of 10 years for Norway or date of first diagnosis of the outcome at study, which-ever is the soonest.

The primary outcome is NDD including ASD, will be defined as a diagnosis of at least one the ICD-10 codes presented in codelist Table 10. Please note that ASD codelist is presented separately in the codelist Table 8, and NDD without ASD in the codelist Table 9.

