#### 9.7.2.2 *Incidence examination*

The cumulative incidence proportion, rate and time to onset of NDD, including ASD will be calculated as well as cumulative incidence proportion for composite CM endpoint and specific CM target body system organ groups based on ICD-10 codes. These statistics will be presented for each overall cohort and separately for offspring *paternally exposed to valproate or lamotrigine/ levetiracetam (composite and separately) in monotherapy 3 months prior to LMP2*.

The cumulative incidence (risk) of the primary outcomes reported each year will be explored by estimating the cumulative incidence of incident reports (plus 95% CI). For purposes of this analysis the denominator is defined according to the population initially at risk at the beginning of the study, since the estimates are cumulative; that is live births for NDD, including ASD and live plus non-live births for CM. The numerator will comprise of counts of incident events as recorded during each year and summed to reflect the cumulative count for all years up to that point. The cumulative incidence proportion will be calculated according to the formula:

$$\left( \frac{\text{Total number of offspring paternally exposed with newly diagnosed outcome during each cumulative year of interest}}{\text{Population initially at risk}} \right) \times 100$$

For each exposure group, the numerator for each year will contain the number of offspring for whom the incident outcome has been recorded in that year and will exclude offspring who have had an outcome previously, within the study period. The denominator will include offspring within the numerator and also offspring who did not have an outcome recorded in the current year or preceding years (i.e. only the ‘at risk’ population will be considered).

The cumulative incidence rate of the primary outcome will be modelled using survival methods and expressed as number of cases per 1000 patients-years at risk (+95%CI). Data may also be stratified according to other relevant strong risk factors for events of interest (age, gender) and stratum-specific incidence rates examined.

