5. *Simple pairwise comparison valproate vs lamotrigine and valproate vs levetiracetam in monotherapy.* Valproate, lamotrigine and levetiracetam are medications with similar indications but that may be systematically prescribed for different type of epilepsy (such as valproate for genetically determined epilepsy and lamotrigine for focal onset epilepsy) and potentially other indications (lamotrigine might be prescribed for bipolar disorder and levetiracetam is not). Moreover, they were licensed in different periods (levetiracetam since 2000; lamotrigine since early 1990s; and valproate since 1967 to

treat epilepsy and since 1995 to treat bipolar disorder) resulting in systematic different in the treated populations. With the objective to evaluate if there is a differential effect of using one or the other comparator, a supplementary analysis will be provided to contrast valproate paternal exposure to separately lamotrigine and levetiracetam paternal exposure for the purpose of both NDD and CM outcome:

- a. Describe the characteristics of mother, father and offspring for both the primary and secondary outcome cohort and separately for paternal monotherapy exposure to individual AEDs (valproate or lamotrigine or levetiracetam).
  - b. Investigate the risk of NDD, including ASD, in offspring paternally exposed to valproate (monotherapy), compared to lamotrigine (monotherapy) treatment at the time of conception.
  - c. Investigate the risk of NDD, including ASD, in offspring paternally exposed to valproate (monotherapy), compared to levetiracetam (monotherapy) treatment at the time of conception.
  - d. Investigate the risk of CM, in offspring paternally exposed to valproate (monotherapy), compared to lamotrigine (monotherapy) treatment at the time of conception, in Norway and Denmark only.
  - e. Investigate the risk of CM, in offspring paternally exposed to valproate (monotherapy), compared to levetiracetam (monotherapy) treatment at the time of conception, in Norway and Denmark only.

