In order to meta-analyse cumulative incidence proportions (for both NDD including ASD and CM composite outcomes), risk ratio estimates will be obtained in each country as the ratio of the risk in the valproate paternally exposed group to the risk in the lamotrigine/levetiracetam paternally exposed group; inverse variance weighting will then be applied to the risk ratios. For cumulative incidence rate (for NDD including ASD composite outcome), the inverse variance weighting method will be applied to rate ratios (obtained as the ratio of the incidence rate in the valproate paternally exposed group to the rate in the lamotrigine/levetiracetam group). Hazard ratios from Cox PH regression analysis will be pooled across the three databases after having applied a logarithmic transformation; OR from logistic regression analysis will also be pooled across the Norway and Denmark databases; inverse variance weighting will be applied to these models' estimates.

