- Hospitalizations and outpatient visits within secondary care are comprehensively covered in the National Patient Registers in Denmark, Norway and Sweden. However, diagnosis of NDD can be challenging, since there is a lack of specific medical tests to diagnoses disorders, especially ASD. Specialists must assess behaviour; anomalies not being evident for a number of years after birth. Indeed, subjects may not receive a final diagnosis until much older. The impact of this study is that there may be differences in the identification of certain disorders over other as well as under-recording. However, this is not expected to be differential between the paternal exposure groups. Nevertheless, when evaluating the quality of the childhood ASD diagnosis in the Danish Psychiatric Central Register, it was found that 94% of the childhood ASD diagnoses met the ICD-10 criteria for a correct diagnosis'(66). Therefore, the identification of ASD cases by ICD-10, as proposed in this study, is valid.
- In the case an offspring may have no contact with the health care system for an extended period time, that individual could potentially experience an outcome before it can be recorded. This could cause a delayed diagnosis observation and immortal time bias.
- All relevant measured covariates will be entered into the model for the primary analysis. However, given that registries may not contain information on all relevant known and unknown confounding variables, residual confounding may still be present in the study results. Descriptive analysis and handling of missing data will be conducted as reported in section 9.7.6.
- It is assumed in these analyses that all prescribed drugs are filled and then taken by patients in a compliant manner. Non-compliance would result in misclassification of exposure and could cause an underestimation of the association between exposure and outcome.
- Failure in family linkage may be a limitation in the proposed analysis, particularly if a high proportion of the eligible population to be included in the study cannot be linked within-family units. Examination of characteristics of excluded subjects from linkage is recommended.
- The descriptive analysis of exposure-discordant siblings will not allow result in conclusions about the underlying causality mechanism.

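### The pooled NDD rate ratio is crude with respect to age, so it can differ from 1 with no drug effect when the groups' birth years differ

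*Protocol*

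**What the plan says.** - **Start of person-time.** Under Section 9.3.2.1 the start of observation "will be defined as the birth date of the offspring from which offspring will be observed for occurrence of the outcome of interest".
- **End of person-time.** Besides diagnosis, death and emigration, follow-up stops on "reaching the age of 12 years for Denmark and Sweden and the age of 10 years for Norway" (Section 9.3.2.1) or at study end: "The study time period ends on 31 December 2018 for Denmark and 31 December 2019 for Sweden and Norway" (Section 9.2.1).
- **Rate.** Section 9.7.2.2: "modelled using survival methods and expressed as number of cases per 1000 patients-years at risk". Stratifying by age or gender is optional there, and yields stratum-specific rates only.
- **Ratio that is pooled.** Section 9.7.6: "the inverse variance weighting method will be applied to rate ratios", each being the valproate group's rate divided by the comparator group's rate. No age bands, standardisation or propensity-score weights are attached to it.
- **Age pattern of the outcome.** Section 9.9.2, on diagnosing NDD, speaks of "anomalies not being evident for a number of years after birth".
- **Calendar time.** Table 4 (Section 9.3.3) lists calendar year of conception as a potential confounder. Section 9.7.5, item 5, says of the three drugs that "they were licensed in different periods (levetiracetam since 2000; lamotrigine since early 1990s", with valproate earlier than both.

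**The concern.** Dividing by person-years corrects for how long children are followed, not for a hazard that changes with age. A child born late in the study window is observed only at young ages; a child born early is observed up to age 10 or 12. If diagnoses are rare in the first years, person-time from late-born children carries few events whatever the father took. If one exposure group has more late births, its crude rate shifts for that reason alone.

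The rate ratio will be pooled over three countries and reported beside the hazard ratio in a safety study requested by a regulator. A ratio away from 1 that only reflects age structure could be read as supporting or contradicting the main result.

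**Working it through.** The protocol gives no figure for this rate ratio, so there is none to reproduce. The check asks what the estimator in Section 9.7.6 returns when the hazard at each age is identical in the two groups.

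**Inputs from the protocol**
- Birth windows for NDD (Section 9.2.1): Norway 2010–2019 (10 years), Sweden 2007–2019 (13), Denmark 1997–2018 (22).
- Age caps: 10 years in Norway, 12 in Sweden and Denmark.
- Reference risk of 4% (Section 9.5), taken as the risk by the maximum age.

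**Assumptions, not in the protocol**
- The shape of the hazard over age.
- The birth trend in each group, linear over the window. Trend A: valproate births flat, comparator births tripling. Trend B: valproate births halving, comparator births tripling.
- No deaths or emigration.

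**Step 1: person-time below age 2, uniform births, ignoring the small loss to events**

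A child born at time b has follow-up f(b) = min(study end − b, age cap).
- Norway: mean follow-up 5 years; mean time below age 2 = (8×2 + 2×1)/10 = 1.8; share 1.8/5 = 36%.
- Sweden: total follow-up per 13 birth-years = 1×12 + 12×6 = 84; below age 2 = 11×2 + 2×1 = 24; share 24/84 = 29%.
- Denmark: total per 22 birth-years = 10×12 + 12×6 = 192; below age 2 = 20×2 + 2×1 = 42; share 42/192 = 22%.

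**Step 2: one case by hand (Norway, trend A, no diagnoses before age 2, flat hazard after)**

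With a flat hazard after age 2, the crude rate is proportional to the share of person-time above age 2. For valproate that share is 1 − 0.36 = 0.64. Let v be the fraction of the window remaining at birth. The comparator birth density is then (3 − 2v)/2 and follow-up is 10v.
- Mean follow-up = 10 × 5/12 = 4.167 years.
- Mean time below age 2 = 2 − ∫₀^0.2 (1 − 5v)(3 − 2v) dv = 2 − 0.287 = 1.713.
- Share below age 2 = 1.713/4.167 = 41.1%; share above = 0.589.
- Null rate ratio = 0.640/0.589 = 1.09.

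**Step 3: all shapes, by numerical integration**

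For each group, rate = Σ w(b)[1 − S(f(b))] / Σ w(b)∫₀^f(b) S(a) da, where w is the birth trend and S the common survival curve. The ratio is the valproate rate over the comparator rate, as Section 9.7.6 defines it.

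| Hazard shape (same in both groups) | Trend | Norway | Sweden | Denmark |
|---|---|---|---|---|
| Constant from birth | A or B | 1.00 | 1.00 | 1.00 |
| Zero before 2, then flat | A | 1.09 | 1.06 | 1.03 |
| Zero before 2, then flat | B | 1.13 | 1.10 | 1.05 |
| Zero before 2, rising to age 7, then flat | A | 1.18 | 1.14 | 1.07 |
| Zero before 2, rising to age 7, then flat | B | 1.27 | 1.21 | 1.11 |
| Zero before 2; 3.7% by age 6, 4% by maximum age | A | 1.04 | 0.99 | 0.97 |

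The last shape borrows the 3.7% that Section 9.5 cites for Danish children up to and including 5 years. That source used a different outcome definition.

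**Step 4: two controls.** With equal birth-year distributions every shape returns 1.00. An age-stratified or age-standardised ratio returns 1.00 in every row, because the hazards at each age are equal by construction.

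**The case against.** **The rate is descriptive.** Section 9.7.2.2 sits under descriptive analyses, and the effect estimate is the propensity-score-weighted Cox hazard ratio with the child's age as time scale, itself pooled in Section 9.7.6. This stands: a reader might infer that the primary analysis is biased, and it is not, at least not by this route. But Section 9.7.6 also commits to a between-group rate ratio and to pooling it, so it is a planned comparison.

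**The direction is not established.** A reader might infer that younger comparator children must push the ratio above 1 and create a false valproate excess. That requires a hazard that is low early and does not fall much later, and no hazard shape is given. The last row of the table reverses the sign in Sweden and Denmark. Nor do the documents show that no NDD can be diagnosed early: the code list includes movement disorders and intellectual disability. A low early hazard is enough for the problem to arise. With 20% of the later hazard present before age 2, trends A and B, and a third in which comparator births start at zero, still give 1.02 to 1.17.

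**The licence dates do not support the largest figures.** If comparator births rose from zero, the rising hazard would give 1.61 in Norway and 1.44 in Sweden. But lamotrigine and levetiracetam were licensed before those windows open in 2010 and 2007. Only in Denmark does a licence date (levetiracetam, 2000) fall inside the window. Those figures are therefore not relied on.

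**Readers will see the age pattern.** The protocol plans a smoothed hazard plot, summaries of age at first diagnosis, and cohort characteristics by age and calendar period. These help interpretation but do not alter the pooled ratio.

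**This is SAP detail.** How person-time is split could be left to the SAP. The estimator itself, however, is stated in the protocol, and as stated it is crude.

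**Conclusion.** The point holds as a limited one. The protocol fixes person-time from birth and a plain ratio of group rates to be pooled. That ratio need not equal 1 under no effect when the hazard varies with age and birth years differ between groups. The protocol makes the first condition plain and the second foreseeable.

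Under the assumed birth trends A and B, the null ratio is about 1.03 to 1.27 for a hazard that is zero before age 2 and then flat or rising. It is 1.00 for a hazard constant from birth, and slightly below 1 in Sweden and Denmark if most diagnoses come between ages 2 and 6. These sizes rest on birth trends and hazard shapes that the documents do not give, so neither a direction nor a single figure should be attached to the point. The age-scaled Cox hazard ratio does not share the problem.

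**What to change.** - In Section 9.7.6, replace the pooled crude rate ratio with an age-adjusted one. Use a Poisson model in each country with log person-years as offset and age-band terms, or rates standardised to a common age distribution. Keep the inverse-variance pooling.
- In Section 9.7.2.2, make reporting of NDD rates by one- or two-year age band firm rather than optional.
- Label any remaining crude rates as descriptive and not for comparison between groups.

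The cost is a wording change and one extra step that splits person-time by age. No new data are needed. Some Danish age bands will have to be merged because results based on fewer than five cases are not released (Section 9.9.1).

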For the time to event analysis of the primary outcome, a semi-parametric Proportional Hazards (PH) regression model will be derived to describe the time to event, which will be presented graphically. At least 10 cases will be required per event for crude estimates. A smoothed estimate of empirical hazard function will also be plotted using an epanechnikov kernel (bandwidth to be determined empirically from data). These will be used to describe how the baseline risk of an event changes over time.

In addition, cumulative incidence proportions for the entire period, 0-12 years for Denmark and Sweden and 0-10 years for Norway, will also be presented; this will be calculated as the

total number of offspring experiencing the outcome (NDD and CM, separately) during the entire follow-up (i.e. the sum of the number of events for the years 0 to 12 for Denmark and Sweden, and 0 to 10 for Norway) divided by the initial number of offspring included at the start of follow-up (i.e., population used in the analysis). Furthermore considering index date in the CM cohort will start before or on date of birth and that patients will be followed up until 12 years of age at maximum (10 years of age for Norway), there will be patients with a follow-up longer than 12 years (10 years for Norway), and therefore cumulative incidence proportion for the entire follow-up will include a longer period than 12 years for Denmark and Sweden (but shorter than 13 years). For Norway, the cumulative incidence proportion for the entire follow-up will include a longer period than 10 years, but shorter than 11 years.

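### The 0–12 year (Norway 0–10) cumulative incidence ignores administrative censoring, so it understates risk, and the risk ratio pooled from it can move away from 1 with no effect

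*Protocol*

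**What the plan says.** Section 9.7.2.2 first says that, for the yearly cumulative figures, "the denominator is defined according to the population initially at risk at the beginning of the study". Two paragraphs later it says of the yearly figures: "The denominator will include offspring within the numerator and also offspring who did not have an outcome recorded in the current year or preceding years". For the whole period (0–12 years in Denmark and Sweden, 0–10 in Norway), total events are "divided by the initial number of offspring included at the start of follow-up".

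Section 9.3.2.1 ends follow-up at the earliest of the first diagnosis, death, emigration, age 12 (10 in Norway), and 31 December 2018 in Denmark or 31 December 2019 in Sweden and Norway. On the study period, section 9.2.1 says "this will start from 01 January 2007 in Sweden, 01 January 2010 in Norway, and 01 January 1997" in Denmark (April 2004 for the malformation outcome). Section 9.2.2.1 admits children born alive within that period.

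Section 9.7.6 takes the proportions into the meta-analysis: "risk ratio estimates will be obtained in each country as the ratio of the risk in the valproate paternally exposed group to the risk" among comparator offspring, with inverse-variance pooling for both NDD and CM.

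**The concern.** A proportion over everyone enrolled estimates the risk to age 12 only if everyone is followed to age 12. Here a child born in 2017 counts in the denominator as though observed event-free for the full period. Neither section 9.7.2.2 nor section 9.7.6 corrects for this.

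Three consequences follow.

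- The absolute risks carry an age label that the data do not reach, and their confidence intervals surround the wrong quantity.
- The two denominators define different statistics. One is fixed at the start; the other removes earlier cases.
- If valproate and comparator children differ in birth year, they differ in follow-up, and the risk ratio absorbs that difference. Calendar year of conception is listed as a potential confounder (Table 4), but these proportions and ratios are not described as weighted or adjusted.

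In a regulatory safety report, a pooled risk ratio could then disagree with the hazard ratio beside it for no reason connected with the drug.

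**Working it through.** The protocol gives no figure for this risk ratio, so there is none to reproduce.

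**Inputs from the protocol.** Birth windows: Denmark 1997–2018 (22 years), Sweden 2007–2019 (13), Norway 2010–2019 (10). Maximum ages: 12, 12 and 10. Reference NDD risk: 4% (section 9.5).

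**Assumptions.** The 4% is reached at the maximum age. The cumulative hazard is H·(age/max)^s, with H = −ln(0.96) = 0.0408 and s = 1, 2 or 3. A larger s means later diagnosis. Births are uniform unless tilted as described below.

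**Step 1: who can be followed to the maximum age.**
- Denmark: born by 31 December 2006, 10/22 = 45%.
- Sweden: born by 31 December 2007, 1/13 = 8%.
- Norway: would need birth by 31 December 2009, before the window opens, so none.

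**Step 2: absolute risk.** Among children not fully followed, follow-up is uniform from 0 to the maximum. Their mean observed risk is the average of 1 − exp(−H·u^s) for u from 0 to 1, which is 2.01%, 1.34% and 1.01% for s = 1, 2 and 3.
- Denmark: (10/22)·4 + (12/22)·(2.01 to 1.01) = 2.92% to 2.37%.
- Sweden: (1/13)·4 + (12/13)·(2.01 to 1.01) = 2.17% to 1.24%.
- Norway: 2.01% to 1.01%.

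**Step 3: risk ratio with no true effect.** The same age-specific risk is used in both groups. Birth density over the window (t from 0 to 1) is exp(−kt) for valproate and exp(+kt) for the comparator. Ranges are over s = 1 to 3.

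| Valproate births earlier by (DK / SE / NO) | Denmark | Sweden | Norway |
|---|---|---|---|
| no gap | 1.00 | 1.00 | 1.00 |
| 1.8 / 1.1 / 0.8 years (k = 0.5) | 1.13–1.21 | 1.18–1.34 | 1.18–1.35 |
| 3.6 / 2.1 / 1.6 years (k = 1) | 1.27–1.47 | 1.38–1.79 | 1.39–1.82 |
| k = 1 reversed (s = 2) | 0.72 | 0.61 | 0.61 |

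**Step 4: does a censoring-aware estimate remove it?** There were 300 null simulations per country at the projected group sizes (k = 1, s = 2). The fixed-denominator ratio averaged 1.43, 1.63 and 1.65 in Denmark, Sweden and Norway. The Kaplan–Meier risk ratio averaged 1.03, 1.01 and 1.04, and the Cox hazard ratio 1.03, 1.00 and 1.01. A nominal 5% test of the fixed-denominator ratio rejected in 31%, 37% and 23% of runs.

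**Step 5: malformations.** If 50–80% of diagnoses are made at birth (assumed), with the rest spread evenly over follow-up, the null ratio is 1.02–1.25 for k = 0.5 to 2 with valproate births earlier.

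**The case against.** The primary analysis does not use this denominator. Section 9.7.3.2.1 rests on a crude and a propensity-weighted Cox model, which accounts for actual follow-up, and section 9.7.2 is headed as descriptive. Hazard ratios and person-time rate ratios are pooled beside the risk ratio. This stands and limits the seriousness. The rate ratio is only partly protected: if the hazard rises with age (s = 2 or 3), it is 1.10–1.30 under the null at k = 1. For CM no time-to-event model is planned, only a proportion and a logistic odds ratio.

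Different maximum ages do not by themselves bias a null ratio, because each ratio is formed within one country. That also stands; the common-age requirement concerns what the pooled figure means.

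A reader might infer that the ratio must exceed 1, because section 9.7.5 (item 5) dates the licences to 1967 for valproate, the early 1990s for lamotrigine and 2000 for levetiracetam, so that comparator children would be born later. The document does not support this. All three drugs were licensed before the Swedish and Norwegian windows opened. Only levetiracetam in late-1990s Denmark is directly affected. Taking levetiracetam births from 2001 and otherwise uniform births, the Danish null ratio is 1.09–1.18 against levetiracetam alone. It is 1.02–1.08 against a comparator assumed to be 25–50% levetiracetam. A larger gap, or any gap in Sweden or Norway, needs a trend in use that the protocol does not give.

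**Conclusion.** The point holds, and it should be fixed; it does not threaten the primary conclusion.

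- **Certain from the text:** the denominator ignores administrative censoring, no Norwegian child is observed to age 10, and section 9.7.2.2 gives two incompatible denominators.
- **Under uniform births and a true 4% risk:** the reported risk is too low in both groups, falling to about 60–73% of its true value in Denmark (2.4–2.9%), 30–55% in Sweden (1.2–2.2%) and 25–50% in Norway (1.0–2.0%).
- **Conditional:** the pooled risk ratio is displaced only if birth years differ between groups, upwards if valproate births are earlier and downwards if later. The protocol gives no birth years by group, so neither direction nor size can be asserted. For CM the displacement is smaller if most diagnoses come near birth.

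**What to change.** In section 9.7.2.2, replace the fixed-denominator formula with 1 − Kaplan–Meier risk, or Aalen–Johansen risk with death as a competing event, with 95% confidence intervals at fixed ages that the cohort actually reaches. State one denominator definition and delete the other.

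In section 9.7.6, pool risk ratios only at a common age observed in every pooled country, which must be below 10 years because of Norway. For NDD, the alternative is to drop the risk-ratio pooling and keep the hazard ratio. Propensity weighting of these curves is optional.

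The cost is standard survival code on data already extracted, plus wording changes in two sections.
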